#### **1.3.1. Known and Potential Benefits and Risks of the Test Investigational Medicinal Product(s)**

Results from Phase 2b clinical studies have demonstrated statistically significant reductions in mean headache hours after 1, 2, and 3 months of sc fremanezumab treatment in patients with chronic migraine and statistically significant reductions in monthly migraine days after 1, 2, and 3 months of fremanezumab treatment in patients with episodic migraine. Results for several secondary/exploratory endpoints also showed fremanezumab to be superior to placebo.

Fremanezumab has generally been well tolerated over the ranges of doses evaluated (single iv infusions at 0.02 to 2000 mg in healthy subjects, multiple iv infusions at 30 to 300 mg in healthy subjects, and multiple sc doses at 225 to 900 mg in healthy subjects and migraine patients). The most common treatment-emergent adverse events across all patients/subjects studied were mild to moderate transient general administration site disorders/reactions. Other commonly reported treatment-emergent adverse events were headache, back pain, and upper respiratory tract infection.

Reports of mild to moderate transient administration site disorders/reactions, including injection site bruising, injection site swelling, administration site pain, injection site pain, injection site pruritus, injection site dermatitis, injection site rash, injection site edema, injection site discomfort, injection site hemorrhage, injection site irritation, injection site mass, and injection site hematoma, have occurred with sc administration. In addition, reports of mild and transient infusion site pain and swelling following iv administration have occurred. Among these events, the following have been identified as adverse drug reactions (identified risks): injection site erythema, administration site pain, injection site pain, injection site pruritus, and injection site dermatitis. None of these identified risks are considered important risks.

Infusion-related reaction and drug hypersensitivity were also identified as adverse drug reactions. To date, 1 subject who received fremanezumab iv had a non-serious infusion-related reaction, and 1 patient who received fremanezumab via the sc route had a non-serious event of drug hypersensitivity. Both events resolved following IMP discontinuation and treatment with diphenhydramine and methylprednisolone. Neither of these identified risks are considered important risks.

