If a patient is withdrawn from the study for multiple reasons that include also adverse events, the termination page of the CRF should indicate that the withdrawal was related to an adverse event. An exception to this requirement will be the occurrence of an adverse event that in the opinion of the investigator is not severe enough to warrant discontinuation but that requires the use of a prohibited medication, thereby requiring discontinuation of the patient. In such a case, the reason for discontinuation would be “need to take a prohibited medication” and not the adverse event.

Should a patient decide to withdraw after administration of the IMP or should the investigator decide to withdraw the patient, all efforts will be made to complete and report all observations up to the time of withdrawal. A complete final evaluation at the time of the patient’s withdrawal should be made and an explanation given as to why the patient is withdrawing or being withdrawn from the study.

The reason for and date of withdrawal from the study must be recorded on the source documentation and transcribed to the CRF. If a patient withdraws consent, every attempt will be made to determine the reason.

All protocol-specified procedures/assessments should be performed at the early withdrawal visit (see [Appendix B](#)). Patients who withdraw from the study will not be replaced. Patients who withdraw early will be offered the opportunity to enter the long-term safety study (Study TV48125-CNS-30058) for the purpose of evaluation of ADAs and safety (adverse events and concomitant medications) approximately 7.5 months after administration of the last dose of IMP in this study. These patients will not receive any doses of fremanezumab after completing participation in the current study and should be treated with standard of care as appropriate. A patient should only be designated as lost to follow up if the site is unable to establish contact with the patient after 3 documented attempts via 2 different methods (phone, text, e-mail, certified letter, etc). In the case of patients lost to follow-up, attempts to contact the patient must be made and documented in the patient’s medical records and transcribed to the CRF.

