### **9.7. Safety Analysis**

Safety analyses will be performed on the safety analysis set (Section 9.2.2). Safety assessments and time points are provided in Table 2.

All adverse events will be coded using the Medical Dictionary for Regulatory Activities. Each patient will be counted only once in each preferred term or system organ class category for the

analyses of safety. Summaries will be presented for all adverse events (overall and by severity), adverse events determined by the investigator to be related to test IMP (defined as related or with missing relationship) (overall and by severity), serious adverse events, and adverse events causing withdrawal from the study. Patient listings of serious adverse events and adverse events leading to withdrawal will be presented.

The use of concomitant medications will be summarized by therapeutic class using descriptive statistics. Concomitant medications will include all medications taken while the patient is treated with IMP.

Changes in laboratory, ECG, and vital signs measurement data will be summarized descriptively. All values will be compared with prespecified boundaries to identify potentially clinically significant changes or values, and such values will be listed.

Safety data will be summarized descriptively overall and by treatment group. For continuous variables, descriptive statistics (n, mean, SD, median, minimum, and maximum) will be provided for actual values and changes from baseline to each time point. For categorical variables, patient counts and percentages will be provided. Descriptive summaries of serious adverse events, patient withdrawals due to adverse events, and potentially clinically significant abnormal values (clinical laboratory or vital signs) based on predefined criteria will also be provided.

If any patient dies during the study, a listing of deaths will be provided, and all relevant information will be discussed in the patient narrative included in the clinical study report.

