### **2. Concomitant Medications Allowed and Disallowed**

#### Steroids:

Screening/run-in period and throughout the study: Systemic steroids are not allowed to be used in the treatment of cluster cycles during the screening/run-in period and for the duration of the study.

The only allowed steroids are intra-articular injection or ocular, ear drops, intranasal, inhaled, and creams for topical use.

Screening/run-in period: Disallowed if patient used systemic steroids to treat the current CH cycle or for any other indication to treat the current CH cycle within  $\leq 7$  days of screening.

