8.3. Adverse Events

Adverse events will be recorded from time informed consent is obtained through the end of study participation.

The following are considered protocol-defined adverse events of special interest to be sent to the sponsor's Global Patient Safety and Pharmacovigilance Department for evaluation: ophthalmic-related adverse events of at least moderate severity, events of possible drug-induced liver injury (aspartate aminotransferase or alanine aminotransferase $\geq 3 \times$ the upper limit of normal [ULN], total bilirubin $\geq 2 \times$ the ULN, or international normalized ratio >1.5), Hy's Law events, or events of anaphylaxis and severe hypersensitivity reactions.

All adverse events will be coded using MedDRA (version 18.1). Each patient will be counted only once in each preferred term or SOC category for the analyses of safety. Summaries will be presented for all adverse events (overall and by severity), adverse events determined by the investigator to be related to test IMP (defined as related or with missing relationship) (overall and by severity), serious adverse events, and adverse events causing withdrawal from the study. Adverse events with the missing flag indicating serious will be excluded from the summary of serious adverse events but included in the summary of non-serious adverse events.

Summaries for injection site and infusion-related adverse events and protocol-defined adverse events of special interest will be presented (overall and by severity).

Listings for deaths, serious adverse events, adverse events leading to discontinuation, injection site and infusion-related adverse events, and protocol-defined adverse events of special interest will be presented. In addition, listings for MedDRA dictionary terms for adverse event descriptions and adverse event preferred terms by patient number and treatment group will be presented.

Spontaneous abortion or an elective abortion due to developmental anomalies will be reported as a serious adverse event (protocol Section 7.2). These serious adverse events will be listed separately if applicable.

Summaries will include treatment-emergent adverse events which are defined as adverse events occurring at or after the first dose of the IMP. The listing will include all adverse events recorded.

Adverse events for patients who did not meet screening criteria will be listed.

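### Protocol Section 4.3 records some withdrawals that began with an adverse event as prohibited-medication withdrawals only, and no planned analysis adds them back

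*Protocol*

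**What the plan says.** For a withdrawal with several reasons, Protocol Section 4.3 sets a conservative default. If an adverse event is among them, "the termination page of the CRF should indicate that the withdrawal was related to an adverse event". It then exempts an event that the investigator considers "not severe enough to warrant discontinuation but that requires the use of a prohibited medication, thereby requiring discontinuation of the patient". In that case "the reason for discontinuation would be “need to take a prohibited medication” and not the adverse event". Item 4 of the withdrawal criteria in the same section makes taking a prohibited medication a ground for withdrawal.

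Three planned outputs use, or may use, the recorded reason:

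- **Disposition.** Protocol 9.4.1 and SAP 5.2 tabulate withdrawals by reason.
- **Safety.** Protocol 9.7 promises descriptive summaries of "patient withdrawals due to adverse events". SAP 8.3 lists among its summaries "serious adverse events, and adverse events causing withdrawal from the study". Neither names the CRF field that identifies these patients.
- **Sensitivity analysis of the primary endpoint.** SAP 6.2.3.1 assigns an active-arm patient to the placebo group for imputation only if the withdrawal reason is an adverse event or lack of efficacy.

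SAP Section 17 declares no changes from the protocol, and no section says how patients coded under the exception are to be handled.

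**The concern.** A patient covered by the exception would not have needed the prohibited medicine without the adverse event, so the event is the first cause of the withdrawal. The protocol nevertheless tells the site not to give it as the reason. This is an explicit instruction and cannot be read as a detail left open for the SAP to fill.

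Two things are at stake. The first is the count of patients who left because of an adverse event, a routine tolerability figure. The second is the imputation rule in SAP 6.2.3.1, which is meant to be cautious about active-arm patients who leave for an adverse event. A recoded patient escapes that caution because of a coding convention.

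**Working it through.** Apart from the planned withdrawal total there is no stated figure to reproduce, so the check is mainly a comparison of sections.

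**1. The chain.** The adverse event occurs. Its treatment is prohibited. Item 4 of the Section 4.3 criteria then applies and the patient is withdrawn. The exception records the third step as the reason and drops the first. It applies only where the investigator judges that the event itself did not warrant stopping.

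**2. Effect on each output.**

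| Output | Does it use the recorded reason? | Effect of the exception |
|---|---|---|
| Disposition by reason (SAP 5.2) | Yes | Adverse-event withdrawals undercounted whenever the exception is used |
| Adverse events causing withdrawal (Protocol 9.7, SAP 8.3) | Not stated | Undercounted if taken from the termination page; not necessarily if taken from the adverse-event record |
| Multiple imputation (SAP 6.2.3.1) | Yes, for active arms only | Recoded active-arm patient is not moved to placebo for imputation |
| Primary ANCOVA (SAP 6.2.2) | No; it prorates available diary data | None |

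**3. Can the patients be recovered?** Yes. Protocol 7.1.2 requires the action taken regarding IMP and the treatment given to be recorded for every adverse event. Protocol 5.6 requires the indication of every concomitant medication. Linking the two identifies a patient whose prohibited medicine was started for an adverse event.

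**4. Size of the undercount.** The plan expects 14% discontinuation: 258 / (1 − 0.14) = 300 randomized. That is 300 − 258 = 42 withdrawals from all causes, or 100 − 86 = 14 per arm. It gives no split by reason and no recoded share, so the undercount cannot be calculated. For scale only, with both inputs assumed:

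reported = true × (1 − recoded share), per 100 patients

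| True number | 10% recoded | 25% recoded | 50% recoded |
|---|---|---|---|
| 2 | 1.8 | 1.5 | 1.0 |
| 4 | 3.6 | 3.0 | 2.0 |
| 6 | 5.4 | 4.5 | 3.0 |

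**5. Size in the imputation.** Assume that placebo-based and own-arm imputation differ by the full planning difference of 4 attacks per month, and that all three months are imputed. Then k recoded patients in an arm of 100 shift that arm's mean by k × 4 / 100. The largest recoded number in the table is 6 × 0.5 = 3, which gives 3 × 4 / 100 = 0.12 attacks per month, against the planning difference of 4. The shift is smaller if some months were observed.

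**The case against.** The strongest reply is that nothing need be lost from the safety reporting. The exception governs the reason for discontinuation, whereas SAP 8.3 describes a summary of adverse events. Every event is still recorded with its treatment and the action taken. Infusion-related, injection-site and special-interest events have their own summaries and listings. This stands in part: a reader might infer that the safety table is certainly under-reported, and the documents do not support that. They leave its source undefined. If it is the adverse-event record, the safety and disposition tables can disagree with no planned reconciliation.

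A reader might also infer that the exception favours the active arms. Protocol 1.3.1 describes one infusion-related reaction and one drug hypersensitivity event on fremanezumab: "Both events resolved following IMP discontinuation and treatment with diphenhydramine and methylprednisolone". Of steroids, Appendix H says: "The only allowed steroids are intra-articular injection or ocular, ear drops, intranasal, inhaled, and creams for topical use". But IMP was stopped in both cases, which fits the general rule better than an exception for events that did not warrant stopping. Significant worsening of the disease under study can also be an adverse event (Protocol 7.1.1), and Appendix H bars systemic steroids for cluster cycles. That route could load on placebo. Investigators are blinded. The direction is therefore undetermined.

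The group may also be very small or empty. Opioids and butalbital are allowed as needed after randomization. Protocol 7.1.8 and Appendix C leave room for a patient to continue after a deviation. Appendix H first bars systemic steroids for cluster cycles and then gives a general list of allowed forms, so the status of a steroid given for an allergic reaction is unclear and those passages must be reconciled. All of this limits the size. None of it removes the coding instruction or its effect on the disposition table and the imputation rule.

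**Conclusion.** The point holds in a limited form. For events within the exception, the undercount in the disposition table follows directly from the protocol's own rule. The undercount in the safety summary is a risk that depends on an unstated source field. The loss of placebo-based imputation applies only to active-arm patients. It makes that sensitivity analysis less cautious if placebo-based values are the less favourable ones, and under the assumptions above the shift is at most 0.12 attacks per month. The primary analysis is untouched.

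The true number of affected patients and their distribution by arm cannot be obtained from the documents, and the number is probably small. The change is still worth making because the rule is explicit, the data to correct it are already collected, and the correction is cheap.

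**What to change.** Keep the recorded reason as Section 4.3 has it, and add to the SAP:

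- **SAP 8.3 and 5.2:** a patient whose prohibited medication was started to treat an adverse event is also counted and listed, by arm, under adverse events causing withdrawal. Derive this from the concomitant-medication indication (Protocol 5.6) and from the treatment and action taken recorded for each adverse event (Protocol 7.1.2). State that derivation as the source for the safety summary.
- **SAP 6.2.3.1:** these patients are handled as adverse-event withdrawals for imputation.

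The cost is one extra derivation, a slightly less favourable count of adverse-event withdrawals, and a sensitivity analysis that may be slightly harder on the active arms. When a patient stops treatment does not change.

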#### **4.4. Replacement of Patients**

A patient who is randomized/enrolled but does not complete the treatment period will not be replaced with another eligible patient.

#### **4.5. Rescreening**

A patient who is screened and does not meet study inclusion and exclusion criteria will not be considered for screening again.

#### **4.6. Screening Failure**

Screening failures are defined as participants who consent to participate in the clinical study but are not subsequently randomized/enrolled in the study. Minimal information includes but is not limited to demography, screening failure details, eligibility criteria, and any adverse events or serious adverse events.

## 5. TREATMENTS

### 5.1. Investigational Medicinal Products Used in the Study

IMP is defined as the test IMP and the placebo IMP. Details of the test and placebo IMPs are presented in [Table 3](#).

**Table 3: Investigational Medicinal Products Used in the Study**

IMP Name	Test IMP	Placebo IMP
Trade name and INN, if applicable, or company-assigned number	Fremanezumab (TEV-48125 [formerly LBR-101, PF-04427429, or RN307])	n/a
Formulation	Solution for injection	Solution for injection
Unit dose strength(s)/Dosage level(s)	225 mg/1.5 mL 900 mg iv loading dose followed by 225 mg sc monthly or 675 mg sc dose followed by 225 mg sc monthly	n/a
Route of administration	Fremanezumab will be administered as iv infusions and sc injections by qualified study personnel at the study center.	Placebo will be administered as iv infusions and sc injections by qualified study personnel at the study center.
Packaging	Fremanezumab will be provided in prefilled syringes contained in uniquely numbered kits and stored (refrigerated at 2°C to 8°C) on site. Prefilled syringes will contain fremanezumab at a concentration of 150 mg/mL.	Placebo will be provided in prefilled syringes contained in uniquely numbered kits and stored (refrigerated at 2°C to 8°C) on site. Prefilled syringes will contain the same vehicle and excipients as those for active infusion and injection.
Manufacturer	Teva Branded Pharmaceutical Products R&D, Inc. [name]	Teva Branded Pharmaceutical Products R&D, Inc. [name]

IMP=investigational medicinal product; iv=intravenous; n/a=not applicable; sc=subcutaneous.

Administration of IMP will be via the iv and sc routes. At visit 2, IMP (test or placebo) will be administered via an approximately 1-hour iv infusion followed by 3 sc injections of IMP (test or placebo). At visits 3 and 4, IMP (test or placebo) will be administered as single sc injections. The recommended sc injection sites follow the National Institutes of Health Patient Education Guidelines of September 2015, which are available in [Appendix U](#) of this document and at the following website: [http://www.cc.nih.gov/ccc/patient\\_education/pepubs/subq.pdf](http://www.cc.nih.gov/ccc/patient_education/pepubs/subq.pdf). The suggested sites of injection are back of upper arms, lower abdomen/belly/waistline, and front of thighs. At each visit, the injections should be given in a different location (eg, not in precisely the same place), and study staff member(s) responsible for administration of injections should inspect previous injection sites to ensure that they are free of bruising and tenderness and that proper

rotation of sites is performed. The total number of sc injections and their locations will be recorded for each dosing visit (visits 2 through 4, test or placebo). A 1.5-mL volume from each prefilled syringe must be injected sc for dosing to be considered complete.

### **5.1.1. Test Investigational Medicinal Product**

Fremanezumab is a fully humanized IgG2a/kappa monoclonal antibody derived from a murine precursor. Fremanezumab for CH is being developed for iv and sc administration.

Additional details may be found in [Table 3](#) and in the IB for fremanezumab.

#### **5.1.1.1. Starting Dose and Dose Levels**

Patients randomized to receive fremanezumab will receive either 900 mg or 675 mg. At visit 2 (week 0), iv administration of treatment (IMP or placebo) will precede sc administration (IMP or placebo). Patients randomized to the 900-mg iv loading dose group will receive 900 mg of fremanezumab as an approximately 1-hour iv infusion followed by 3 placebo sc injections at visit 2 (week 0) and fremanezumab at 225 mg administered as single sc injections (225 mg/1.5 mL) at visits 3 and 4 (weeks 4 and 8, respectively). Patients in the 675-mg sc dose group will receive placebo as an approximately 1-hour iv infusion followed by fremanezumab at 675 mg administered as 3 sc injections (225 mg/1.5 mL) at visit 2 (week 0) and fremanezumab at 225 mg administered as single sc injections at visits 3 and 4 (weeks 4 and 8, respectively).

#### **5.1.2. Placebo Investigational Medicinal Product**

The placebo will be the same vehicle and excipients as those for fremanezumab. See [Table 3](#) for additional details. Patients randomized to the placebo group will receive placebo administered via an approximately 1-hour iv infusion followed by placebo as 3 sc injections at visit 2 (week 0) and placebo administered as single sc injections at visits 3 and 4 (weeks 4 and 8, respectively).

### **5.2. Preparation, Handling, Labeling, Storage, and Accountability for Investigational Medicinal Products**

Information pertaining to the preparation, handling, labeling, storage, and accountability for the IMP used in this study can be found in [Appendix G](#).

### **5.3. Justification for Investigational Medicinal Products**

#### **5.3.1. Justification for Dose of Test Investigational Medicinal Product**

The fremanezumab doses, regimens, and routes of administration to be evaluated in this double-blind, double-dummy, placebo-controlled study were selected on the basis of 3 key factors. First, simulations suggest that  $C_{max}$  is the most significant pharmacokinetic parameter in the efficacy of fremanezumab (in migraine). As CH is considered one of the most severe forms of pain a person can experience, treatments that provide quick and lasting relief (ie, for the duration of the cluster period) are a priority for this patient population. Second, the biological nature of the disease mandates the need for any treatment to desensitize the third order neuron, not the second (as is the case in migraine), suggesting that high levels of blockade at the first neuron would be necessary. Third, the favorable safety profile of the drug, as well as clinical and

nonclinical safety data on exposure, suggest that the proposed doses, regimens, and routes of administration will not present any safety concerns.

In the current study, high doses are planned for the first dose (900 mg iv or 675 mg sc) in order to provide a rapid response, especially following iv infusion where higher peak plasma  $C_{max}$  generally occurs at or shortly after the end of infusion compared with 5 to 7 days postdose for sc injections. The 2 forms of loading dose will provide data to confirm the benefit of either the iv or sc as loading dose. Monthly doses of fremanezumab at 225 mg sc were added to both the initial dose of 900 mg iv and 675 mg sc for maintenance of efficacy. Based on modelling, the inclusion of a loading dose should allow patients to reach steady state faster. The monthly doses of 225 mg sc in this CCH population will account for the continuous attacks, with less than 1 month free of headaches between attacks, seen with this CH form.

